2. At ~6am subjects are given a priming dose of [15N]-Phe (0.7 mg/kg), followed by continuous infusion over the next 8 hours of 15[N]-Phe (0.7 mg/kg).
3. 2H5-Phe infusion begins at time 0 and continues for 5hr at a variable rate to mimic meal 13C6-Phe Ra.
4. During the second phase of the study, CF patients will have been receiving insulin (basal or bolus) or placebo for 1 month. They will receive their usual insulin/placebo dose during the protein turnover study.
5. To calculate protein dynamics, free amino acids are extracted from plasma using acetic acid and analyzed as their t-butyldimethylsilyl ester derivatives. The molar percent excess (MPE) of phenylalanine isotopes will then be calculated above background

4.2. Drug/Device Handling: Study drug, insulin or placebo (insulin diluent) will be obtained from the manufacturer in standard insulin vials. The investigational pharmacy will cover the label so that the study medication will be blinded.

- IDS #4817

5. Procedures Involved

5.1. Study Design: This double-blind, placebo-controlled trial of insulin therapy in CF youth with abnormal glucose tolerance will assess the impact of 2 different insulin regimens on protein turnover. In Phase 1, stable isotope measurement of meal-stimulated protein flux will be done in CF patients and normal controls, followed by bi-weekly fasting blood draws x2 wks to assess individual proteins. In Phase 2, CF patients will receive once daily basal insulin, 3X daily rapid-acting insulin, or injectable placebo for 6 weeks. After the 1st month, the meal-stimulated protein flux study will be repeated, followed by bi-weekly fasting blood draws x2 wks to assess individual proteins. Power analysis suggests 15 patients are needed per group; 20 are planned to account for drop-outs due to acute illness and non-adherence (although we expect good adherence since the treatment period is short).

5.2. Study Procedures:

Phase 1: Baseline Assessment, No insulin therapy, All CF patients and controls will complete this phase

PROTOCOL TITLE: The Impact of Insulin Therapy on Protein Turnover in Pre-Diabetic Cystic Fibrosis Patients

VERSION DATE: 28 June 2021

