insulintherapy. They could also have hypoglycemic reactions during the jello part of the study. This will be closely monitored and they will receive juice if symptoms arise.

2. There is potential for discomfort as the iv is being inserted and at the iv site.

3. The stable isotopes to be infused are naturally occurring isotope of amino acids and thus the amino acids are not anticipated to pose any risk. During preparation of any iv solution there is the potential for contamination which is why the isotopes will be prepared by the investigational pharmacy under their usual sterile protocol.

4. Confidentiality may be breached.

5. Nausea from eating the Jello.

6. DXA is an x-ray that has very little radiation exposure.

7. The continuous glucose monitor may cause some discomfort, inflammation or irritation at the site.

13. Potential Benefits to Participants

13.1. Potential Benefits: It is possible that there is no benefit for participants because they may not receive active drug. There is a possibility that insulin replacement therapy may be effective in breaking the cycle of underweight and overall clinical deterioration because of its potent anabolic effects on protein turnover.

14. Statistical Considerations

This study will compare the three parallel treatment groups (placebo, basal insulin, and pre-meal insulin) on the basis of within-subject changes from week 0 (baseline) to week 8 (after 1 month of assigned treatment). The primary endpoints are within-subject differences from week 0 to week 8 in protein turnover parameters, change in Phe flux (ΔQP) and in conversion of Phe to Tyr (ΔQPT). Treatment groups will be compared by pairwise contrasts in analysis of variance, adjusted for baseline protein turnover. The primary-endpoint analysis will be per-protocol, performed on adherent subjects who received at least 70% of study medication in order to assess insulin effects. In addition, as part of planning for a larger trial, an intent-to-treat analysis will be performed, including all randomized participants to assess insulin treatment effects in practice. Exploratory analyses will examine associations between differences in protein turnover parameters and mechanistic endpoints: baseline pulmonary function, BMI percentile, dietary intake (from diet records), observed plasma glucose mean and MAGE (from CGM), cytokines, and treatment adherence.

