
We anticipate that 45 participants, 15 from each of 3 arms, will provide sufficient power to detect clinically significant improvements in protein turnover (ΔQP and ΔQPT) at baseline, based on comparisons between healthy controls and insulin-insufficient CF patients in our previous study (18). Details are given below. We have inflated the sample size to 20 per arm to allow replacement of drop-outs and non-adherent participants, participants who develop diabetes, or suffer an acute exacerbation. The most common reason for drop out is likely to be acute illness, although the brief (3 month) time span will help reduce this. Also, given the short time span of this study we anticipate adherence will be good. This is in line with other studies in CF where about 80% of subjects are adherent at least 80% of the time (24, 65). Because many of our subjects will be adolescents, one might expect somewhat worse adherence. However, we believe this will be offset by the short duration of the study and by mechanisms to encourage adherence such as school nurse supervision on school days and frequent contact with study personnel. Study drop-out may occur due to development of fasting hyperglycemia or acute illness. These are discussed in greater detail in the human

PROTOCOL TITLE: The Impact of Insulin Therapy on Protein Turnover in Pre-Diabetic Cystic Fibrosis Patients

VERSION DATE: 28 June 2021

subjects section. We expect less than 2% of subjects to develop CFRD during the 3 month study period. Patients who experience acute illness during the study may repeat it when they are well. Thus, we have inflated our group size to account for 20% non-adherence, 1-2% development of diabetes, and 11-12% acute illness.

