Because studies of the effect of chronic insulin therapy have not been conducted previously in CF patients, precise estimates of treatment effect cannot be made. We previously demonstrated significant insulin treatment effects protein on *de novo* synthesis in 14 non-CF study participants, 7 with type 1 diabetes and 7 without (66). Previous work (24) gave estimates for CF patients of the standard deviation (SD) of changes in protein turnover parameters ΔQP and ΔQPT , differences between conditions of insulin infusion and baseline fasting. The primary endpoint is the within-subject change in ΔQP and ΔQPT from week 0 (baseline) to week 8 (after 1 month of assigned treatment), and we estimated the SD of these changes as $(SD \text{ of } \Delta QX) \sqrt{2(1 - \rho)}$, assuming $\rho=.6$ for within-subject correlation, for $\Delta QP = 4.0$ and $\Delta QPT = 1.26$. The table below reports these standard deviations and shows corresponding minimum differences that the study would have 80% power to detect with sample sizes of 15 or 20 in each group. For context, these minimum detectable differences are also given as percent of the baseline value in the CF patients. Observed mean differences in ΔQP and ΔQPT between CF patients and healthy controls were *larger* than the minimum detectable differences for $n = 15/\text{group}$ (24). To the degree that either insulin treatment is able to normalize protein turnover in the CF patients, these observed differences suggest possible treatment effects.

N per group	Minimum detectable	Minimum detectable difference as % of	Observed mean difference (CF patients –
ΔQP (SD = 3.6)		baseline mean = 50.8	6.0
15	3.8	7%	
20	3.3	6%	
ΔQPT (SD =		baseline mean = 6.43	1.5
15	1.2	19%	
20	1.0	16%	

The unblinded study statistician will perform new sample size calculations after the first 15 CF subjects (5 in each group), and, if necessary, additional subjects will be studied.

15. Confidentiality

PROTOCOL TITLE: The Impact of Insulin Therapy on Protein Turnover in Pre-Diabetic Cystic Fibrosis Patients

VERSION DATE: 28 June 2021

15.1. Data Security: The PI, [name], will store and maintain data indefinitely on her password protected UM desktop computer in her locked office which is maintained by the AHC.

16. Provisions to Monitor the Data to Ensure the Safety of Participants

16.1. Data Integrity Monitoring.

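### Section 14: at the plan's own loss rates, 20 per arm leaves 13-14 evaluable participants, not the 15 the power analysis requires; the effect on power is modest

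*Combined protocol and SAP*

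**What the plan says.** Section 5.1 gives the target and the inflated size: "Power analysis suggests 15 patients are needed per group; 20 are planned to account for drop-outs due to acute illness and non-adherence". Section 14, Power Analysis, repeats this ("We have inflated the sample size to 20 per arm to allow replacement of drop-outs and non-adherent participants") and lists the losses covered: "we have inflated our group size to account for 20% non-adherence, 1-2% development of diabetes, and 11-12% acute illness".

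Three other statements bear on how many participants will be evaluable.

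- The primary analysis excludes non-adherent participants: "The primary-endpoint analysis will be per-protocol, performed on adherent subjects who received at least 70% of study medication".
- The support for 20% non-adherence is a figure from other CF studies, where "about 80% of subjects are adherent at least 80% of the time". That is a stricter cut than the 70% used for exclusion.
- On illness, Section 14 says "Patients who experience acute illness during the study may repeat it when they are well". Section 11.1 says participants who fall ill will be withdrawn, and Section 11.2 says they may be contacted about restarting.

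The table of minimum detectable differences has rows for 15 and 20 per group only.

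**The concern.** An allowance for losses has to be worked back from the number enrolled. If a fraction d is lost, N enrolled leave N(1 - d), so the enrolment needed is the target divided by (1 - d). Multiplying the target by (1 + d) always falls short, and the shortfall is visible when d is about one third. The document prints no inflation formula, but 20 is what multiplication gives.

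The evaluable count matters here because the primary comparison is per-protocol: a non-adherent participant leaves it altogether. If the plan's rates are right, the trial will have fewer evaluable participants per arm than either row of its table describes.

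**Working it through.** **Inputs (Section 14).** Target 15 per arm; enrolled 20 per arm; losses 20%, 1-2% and 11-12%; SDs 4.0 (ΔQP) and 1.26 (ΔQPT); within-subject correlation ρ = 0.6; power 80%; reference differences 6.0 and 1.5. Alpha is not stated; two-sided 0.05 without multiplicity adjustment is assumed.

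**1. Reproducing the plan's figures.**

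- Total loss: 20 + 1 + 11 = 32%, up to 20 + 2 + 12 = 34%.
- 15 × 1.32 = 19.8 and 15 × 1.34 = 20.1, which match the stated 20.
- SD of change: 4.0 × √(2(1 − 0.6)) = 3.58 and 1.26 × √0.8 = 1.13.
- A two-sample noncentral t calculation with 2n − 2 degrees of freedom gives detectable differences of 3.79 and 1.19 at n = 15, and 3.25 and 1.02 at n = 20. The table prints 3.8 and 1.2, and 3.3 and 1.0, so the alpha assumption fits.

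**2. What 20 per arm delivers.**

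| Losses | Share retained | Left from 20 | Enrolment needed for 15 |
|---|---|---|---|
| Additive, low | 0.68 | 13.6 | 15/0.68 = 22.1 |
| Additive, high | 0.66 | 13.2 | 15/0.66 = 22.7 |
| Independent, low | 0.80 × 0.99 × 0.89 = 0.705 | 14.1 | 21.3 |
| Independent, high | 0.80 × 0.98 × 0.88 = 0.690 | 13.8 | 21.7 |

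**3. What would make 20 enough.** Keeping 15 of 20 allows a total loss of 25%.

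- *Repeats alone.* Additive: (0.32 − 0.25)/0.11 = 64% to (0.34 − 0.25)/0.12 = 75% of ill participants must repeat and become evaluable. Independent: 52-64%.
- *Adherence alone.* Additive: non-adherence at the 70% cut of at most 0.25 − 0.14 = 11% to 0.25 − 0.12 = 13%. Independent: 1 − 0.75/(0.98 × 0.88) = 13% to 1 − 0.75/(0.99 × 0.89) = 15%.
- *A mix.* At 16% non-adherence, 27-42% of ill participants must repeat (11-26% if independent). At 18%, 45-58% (31-44%).

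**4. Consequence, unadjusted change scores (the basis of the printed table).**

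| n per arm | Detectable ΔQP / ΔQPT | Power at 3.8 / 1.2 | Power at 6.0 / 1.5 |
|---|---|---|---|
| 13 | 4.10 / 1.29 | 74% / 74% | 98% / 90% |
| 14 | 3.94 / 1.24 | 77% / 77% | 99% / 92% |
| 15 | 3.79 / 1.19 | 80% / 80% | 99% / 94% |

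With the SD rounded to 3.6, power at 3.8 is 73% (n = 13) and 77% (n = 14). The detectable differences at 13-14 are 4-8% above those at 15, and are about 8% (ΔQP) and 19-20% (ΔQPT) of the baseline means of 50.8 and 6.43.

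**5. Consequence, the planned analysis.** The plan says "Treatment groups will be compared by pairwise contrasts in analysis of variance, adjusted for baseline protein turnover". With equal variances at the two visits, the residual SD is SD × √(1 − ρ²): 4.0 × 0.8 = 3.20 and 1.26 × 0.8 = 1.008, with 3n − 4 degrees of freedom. Detectable differences are 3.62/1.14 at n = 13, 3.48/1.10 at n = 14 and 3.35/1.06 at n = 15. Adjusted power at a ΔQP difference of 3.8:

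| ρ | n = 13 | n = 14 | n = 15 |
|---|---|---|---|
| 0.4 | 73% | 76% | 79% |
| 0.5 | 78% | 81% | 84% |
| 0.6 | 84% | 87% | 89% |
| 0.7 | 91% | 93% | 95% |

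For any ρ from 0.4 to 0.7, going from 15 to 13-14 costs 2-6 points.

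**The case against.** The strongest reply is that the planned analysis keeps its promise anyway. With baseline adjustment at ρ = 0.6, 13-14 per arm detects 3.5-3.6 and 1.10-1.14, better than the printed n=15 row, and power at 3.8 is 84-87%. The 73-77% belongs to an unadjusted test, at a difference that gives 80% at n = 15 by construction. The plan also notes that "Observed mean differences in ΔQP and ΔQPT between CF patients and healthy controls were" larger than the n=15 detectable differences, and at those values power is high throughout. All of this stands, and it is why the effect is called modest. It does not make 20 the right inflation for the stated losses.

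The other replies stand in part.

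- *Illness repeats.* If every ill participant repeated successfully, loss would be 21-22% and 15.6-15.8 would remain. But no repeat share is given, and Section 14 still counts the full 11-12% as loss.
- *Adherence.* Non-adherence at a 70% cut may well be below a rate taken from an 80% cut. But the plan budgets 20%.
- *Overlapping causes.* If 64-75% of illness losses fell among the non-adherent, 15 would remain. The plan lists the causes separately, and their simple sum reproduces its 20.
- *Re-estimation after 15 CF participants.* It allows more participants, but no rule ties it to the evaluable count.
- *The study-wide 100 in Section 21.1.* If 20-30 of these are controls and the rest are randomised CF patients (an assumption), (100 − 30)/3 × 0.66 = 15.4 to (100 − 20)/3 × 0.68 = 18.1 per arm would remain. But the aims plan 60 CF participants, and Sections 5.1 and 14 plan 20 per arm.

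That 20 was obtained as 15 × 1.33 is an inference from the match. The shortfall does not depend on it.

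**Conclusion.** The concern holds. At the loss rates Section 14 states, 20 per arm yields 13.2-13.6 evaluable participants if the losses add, or 13.8-14.1 if they are independent. Keeping 15 would take 22-23 per arm (about 22 if independent). The gap closes only with repeat or adherence rates the plan does not state, or with losses that overlap heavily.

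The cost is small: 3-7 points of unadjusted power at the printed n=15 differences, 2-6 points in the adjusted analysis, and little at the reference differences. It is an error in the stated justification that should be corrected. It does not show that the trial is underpowered. The power figures rest on two-sided 0.05; the adjusted ones also rest on equal variances at the two visits. The intent-to-treat analysis, which includes all randomised participants, does not lose the non-adherent in this way.

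**What to change.** Do one of two things in Section 14.

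(a) State the expected evaluable number as 13-14 per arm and add the matching row to the table, labelled either unadjusted (3.9-4.1 for ΔQP, 1.24-1.29 for ΔQPT) or baseline-adjusted at ρ = 0.6 (3.5-3.6 and 1.10-1.14).

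(b) State the non-adherence rate expected at the 70% cut and the share of ill participants expected to repeat that together keep 15 per arm, for example one of the mixes worked out above. Section 9.1 reports 40 CF patients consented and Section 16.2 reports 24 subjects studied, so losses observed so far could inform these rates.

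Option (a) is the simpler and needs no new assumption. In either case it would help to reconcile Sections 11.1 and 11.2 with the illness provision in Section 14, and to say how a participant who repeats is counted.

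The cost is one sentence and, for (a), one table row, with no change of design. Enrolling 22-23 per arm would mean 6-9 more CF patients and is not asked for, given the modest effect. The drawback of (a) is a slightly larger printed unadjusted difference. The drawback of (b) is committing to rates for which the plan cites no figure at the 70% cut.

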Randomized into group (once daily basal insulin, 3x daily rapid acting insulin, or placebo) Insulin (basal or rapid) or placebo, will be supplied by the manufacturer in identical standard insulin vials. Participants will be instructed in subcutaneous injection technique. Study medication adjustments will be made under the supervision of the research teams, who are quite familiar with insulin management in patients with CF, and who will be available at all times for support.

PROTOCOL TITLE: The Impact of Insulin Therapy on Protein Turnover in Pre-Diabetic Cystic Fibrosis Patients

VERSION DATE: 28 June 2021

Visit 3 (Week 6, +/- 7 days): Complete the meal-stimulated protein flux study part again from Phase 1 along with the DXA scan, CFQ-R, and CGM placement. There will not be a dietitian consult at this visit.

Visit 4 (Week 7, +/- 1 day): outpatient blood draw to assess individual proteins and removal of continuous glucose monitor

Visit 5 (Week 8, +/- 1 day): outpatient blood draw to assess individual proteins and end study.

Between Visits:

Study personnel will contact (e.g. telephone, email) patients every three days while insulin is being adjusted and weekly thereafter in addition to their study visits. During these contacts staff will review and adjust (if needed) the medication dose, review hypoglycemia symptoms and management, monitor acute illness or adverse events, provide education, and encourage adherence.

[figure not shown]
Participants will also be asked record their blood glucose levels at random times during the entire study. These need to be recorded to determine clinically if insulin adjustment is necessary.

Patients will receive all usual CF care; study participation will not impact standard-of-care treatment.

PROTOCOL TITLE: The Impact of Insulin Therapy on Protein Turnover in Pre-Diabetic Cystic Fibrosis Patients

VERSION DATE: 28 June 2021

5.3. Study Duration: Each study participant will be in the study for an 8 week duration.

- Anticipated duration to recruit all study participants is 4.5 years.
- The anticipated duration to complete all study procedures, including any long-term follow-up, and data analysis is 5 years.

5.4. Individually Identifiable Health Information: Research participants in this study will sign an Authorization to Use or Disclose Protected Health Information for Research Purposes.

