PROTOCOL TITLE: The Impact of Insulin Therapy on Protein Turnover in Pre-Diabetic Cystic Fibrosis Patients

VERSION DATE: 28 June 2021

8.3. Screening: Screening begins with identification of eligible subjects using the standard OGTT recommended annually for all CF patients. Currently at UMN we have 121 CF patients age 10-25, 58 of whom have IGT or INDET and meet study entrance criteria. Nine new patients per year in this age range are diagnosed with IGT or INDET at UM and thus become eligible for the study. An additional 46 non-diabetic children and youth age 10-25 years are followed at our Children's Hospitals and Clinics of Minnesota CF affiliate, 20 of whom currently have abnormal glucose tolerance. Three to four new patients per year become eligible. Our experience from previous CF studies in this age group suggests ~60% will agree to participate. Over the study period we anticipate that 45-50 CF patients will participate from UM and 10-15 from Children's. Normal control subjects will be recruited from fliers placed in the clinics and the University campus. In addition, siblings of CF participants will be invited to participate as controls. CF subjects will be randomized in a 1:1:1 ratio to basal insulin, pre-meal insulin, or injectable placebo (half 3x/daily pre-meal, half 1x/daily), stratified by 2 age intervals (10-17, 18-25y) and gender. Randomization will be done with computer-generated lists for each strata, in randomly alternating blocks of 3 and 6. The research subject, investigator and clinic personnel will be blinded to assignment. Healthy controls will be matched for gender, age and BMI percentile. The statistician will review control recruitment after every 5 subjects to ensure they are representative of the patient groups and determine whether specific control ages or genders should be recruited.

8.4. Vulnerable Populations:

- Children
- Pregnant women/Fetuses/Neonates
- Prisoners
- Adults lacking capacity to consent and/or adults with diminished capacity to consent, including, but not limited to, those with acute medical conditions, psychiatric disorders, neurologic disorders, developmental disorders, and behavioral disorders
- Approached for participation in research during a stressful situation such as emergency room setting, childbirth (labor), etc.
- Disadvantaged in the distribution of social goods and services such as income, housing, or healthcare

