Ideally, both custodial parents or guardians would be present in person at a study visit. However, if one parent is unable to attend a visit in person the signature can be obtained on a remote basis. In general, this is done by providing the study materials (handbook, consent forms) to the parent and then speaking to the second parent by phone to provide fully informed consent.

After discussing the study and answering questions, the signed consent form can be returned (sent via mail, email, or fax) or brought to the study visit by the other responsible parent. If the signature dates are different (which is likely), an explanation that the remote signature was collected off site should be noted in the source document. If, in rare cases, one of the custodial parents is not available despite efforts to reach them (e.g. active duty), this should be documented in a note to file.

19.3 Non-English Speaking Participants: We have a translated parental consent form for those patients that have Spanish speaking parents to abide by our unexpected encounter that we will have used the short form on.

20. Setting

20.1. Research Sites:

- [name] maintains the CF OGTT Database and follows these patients clinically and will identify potential subjects through this.
- Research procedures will take place at the University of Minnesota Health Clinical Research Unit (M Health CRU) as well as at the Delaware Clinical Research Unit (DCRU).
- School-aged participants who are randomized into the pre-meal insulin arm will require the school to assist in the proper storage and overseeing the administration of the required insulin dosage.

21. Multi-Site Research

21.1. Study-Wide Number of Participants: 100-- number is high in case of drop outs, especially due to acute illnesses which are common in CF patients

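### Section 20.1 ties school storage and dose oversight to the pre-meal insulin arm rather than to the injection schedule, which conflicts with the blind and with Section 14 for school-aged three-times-daily participants

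*Combined protocol and SAP*

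**What the plan says.** Section 20.1 (Research Sites) contains the only operational sentence on school dosing: "School-aged participants who are randomized into the pre-meal insulin arm will require the school to assist in the proper storage and overseeing" doses. The sentence goes on to describe what the school oversees as "the administration of the required insulin dosage". It names an arm and a product, and does not mention placebo.

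Section 8.3 (Screening) sets out allocation. CF participants are "randomized in a 1:1:1 ratio to basal insulin, pre-meal insulin, or injectable placebo (half 3x/daily pre-meal, half 1x/daily", so pre-meal insulin is one arm and placebo another, and half the placebo arm shares the pre-meal schedule. The same section states: "The research subject, investigator and clinic personnel will be blinded to assignment".

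The product is masked to match. Section 5.2 says that insulin or placebo "will be supplied by the manufacturer in identical standard insulin vials", and Section 4.2 says: "The investigational pharmacy will cover the label so that the study medication will be blinded".

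The power analysis in Section 14 expects adolescent adherence to be helped by "mechanisms to encourage adherence such as school nurse supervision on school days and frequent contact with study personnel". That sentence has no arm restriction. Section 14 also makes the primary analysis per-protocol, in participants who received at least 70% of study medication. It adds an intent-to-treat analysis of everyone randomized and a comparison of non-adherence between treatments.

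**The concern.** Participants know how often they inject, so the blind can work only within a schedule: pre-meal insulin against three-times-daily placebo, and basal insulin against once-daily placebo. A school rule defined by treatment cuts across the first of these pairs.

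Two things are at stake. First, if school support goes only to participants on pre-meal insulin, its presence or absence shows anyone who knows the rule what a school-aged three-times-daily participant is taking. Secondly, Section 14 counts school supervision as an aid to adherence. Giving it on insulin and withholding it on matching placebo would make adherence depend partly on a study procedure that differs by treatment. The primary analysis selects participants on adherence, and adherence is itself compared between treatments, so both could be affected.

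**Working it through.** The plan gives no figure for this point, and no sample-size figure depends on it. The check sets the sections side by side and adds a little arithmetic.

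**1. Can blinded staff apply the rule?** Section 20.1 requires knowledge of who is in the pre-meal insulin arm. Section 8.3 withholds that from the investigator and clinic personnel, and Sections 4.2 and 5.2 mask the vials. The only role the protocol calls unblinded is the study statistician (end of Section 14), who is given no task with schools; nor is the investigational pharmacy. As written, blinded staff could not carry out the rule.

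**2. What would following it reveal?** Inputs: 20 planned per arm (Section 14) and half of placebo on three daily injections (Section 8.3).

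- Three-times-daily group: 20 insulin + 20 × 1/2 = 10 placebo, total 30.
- Chance of insulin given the schedule alone: 20/30 = 0.67.
- Chance of insulin for a school-aged participant if the rule is followed literally: 1 with school oversight, 0 without it.

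**3. How many participants?** The school-aged share is not given. Assumed shares, applied equally to insulin and placebo:

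| Assumed share | Insulin (of 20) | Placebo (of 10) | Total (of 30) |
|---|---|---|---|
| 25% | 5 | 2.5 | 7.5 |
| 50% | 10 | 5 | 15 |
| 75% | 15 | 7.5 | 22.5 |

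Section 8.3 stratifies at 10-17 and 18-25 years, and Section 16.1 aims for similar numbers of pediatric and young adult participants, so the middle row is plausible. Neither section defines who is school-aged.

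**4. What room does the 70% threshold leave?** Assume one dose per school day, five school days a week, and the same pattern every week. None of this is in the documents.

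- Weekly doses: 3 × 7 = 21.
- Doses needed: 0.70 × 21 = 14.7, so 15. Six may be missed.
- A participant who misses all five school doses has 16/21 = 76% and remains in the per-protocol set. One further missed dose gives 15/21 = 71%, still in; two give 14/21 = 67%, out.
- A participant whose five school doses are all given may miss six of the other 16.

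Lost school doses alone therefore exclude nobody, but they use five of the six permitted misses. The documents give no adherence rate by supervision status, so neither a difference in inclusion nor a bias in the treatment effect can be computed.

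**5. Do the sections agree?** The power analysis describes school supervision without an arm limit; Section 20.1 limits it to pre-meal insulin. The plan is inconsistent on who receives it.

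**The case against.** The strongest reply is that Section 20.1 is loosely worded. It is a logistics bullet under Setting, not an allocation or adherence rule. The protocol elsewhere uses the word insulin for blinded study drug in every arm: Section 5.2 titles Phase 2 as insulin therapy although it covers all three groups, and refers to contacts during insulin adjustment without separating placebo. Blinded staff holding masked vials know only the schedule, so in practice they would probably arrange school support for anyone injecting before meals. This may well be what was meant. It stands as a reason for moderate confidence, but the documents do not settle it, and a school request that names insulin would still misdescribe placebo.

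Some safeguards are also real. The intent-to-treat analysis does not select on adherence, the comparison of non-adherence might reveal a difference, and the group modelling the mass spectrometry data is blinded to arm (Section 16.1). They limit the effect on measurement and selection. They do not restore the blind for participants or staff.

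A reader might infer more than the text supports:

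- *That someone has already been unblinded.* No section gives anyone that task or reports that it happened.
- *That supervision is confined to insulin throughout the plan.* Section 14 sets no such limit.
- *That all three-times-daily participants are exposed, or that the only blindable comparison is lost.* Enrolment runs to age 25, and basal insulin against once-daily placebo is untouched.
- *That adherence is pushed in opposite directions.* Supervision might raise it on insulin; nothing in the rule lowers it on placebo.
- *That unsupervised participants fall out of the primary set.* At 76% they stay in unless they also miss other doses.

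**Conclusion.** The sentence in Section 20.1 is wrong as written. It defines a study procedure by treatment in a trial that blinds those who would carry it out, it leaves out placebo participants on the same schedule, and it disagrees with Section 14. Followed literally, it would disclose assignment for school-aged three-times-daily participants and give unequal adherence support ahead of a primary analysis that selects on adherence.

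The reach is limited to the school-aged part of a planned 30 participants, about 8 to 23 under assumed shares of 25% to 75%, taking an exact half split of a 20-person placebo arm. The size of any bias is unknown. The conclusion depends on the sentence being followed as written; if it was meant as shorthand for the pre-meal schedule, the fault is one of wording. It is worth correcting in either case, because the text permits the harmful reading.

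**What to change.** Reconcile Sections 8.3, 14 and 20.1 by stating the rule by assigned injection schedule. Section 20.1 could refer to *school-aged participants on the three-times-daily schedule, insulin or placebo*, and to study medication in place of insulin dosage. Section 14 can then point to that rule.

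School paperwork should describe the product as blinded study medication that may be insulin or placebo. The protocol names hypoglycemia as the main risk, so schools should not be left unaware that the product may be insulin.

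The cost is one sentence, plus school arrangements for school-aged three-times-daily placebo participants: 2.5 to 7.5 of 10 under the shares assumed above. Sample size and analysis do not change. Section 9.1 reports 40 CF patients already consented, and new wording cannot alter arrangements already made for them. The sponsor should therefore record how school support has been arranged so far, without disclosing assignments to blinded staff, so that any difference can be considered when the per-protocol results are read.
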